## **8.6. Analysis for Calculation of Absorbed Doses to CSF and Blood (Part 1 only)**

The mean absorbed radiation dose in CSF and blood will be calculated from radioactivity measured in CSF and blood samples taken at predefined timepoints after the dosimetry and the treatment doses in Cycle 1.

Analysis of lutetium-177 activity in blood and CSF will include derivation of best-fit uptake and/or clearance parameters (elimination half-times, maximum value) of time-activity curves and of residence times (i.e., cumulated activity in  $\mu\text{Ci}\cdot\text{h}/\text{g}$ ). Blood and CSF time-activity curves will be modeled using exponential retention functions to estimate clearance following the last sampled timepoint, and cumulated activities for both will be computed using a combination of trapezoidal integration of sampling data and analytical integration of clearance curves (re-incorporating physical decay). Absorbed doses in the blood and CSF will then be derived from cumulated activity by applying the equilibrium absorbed dose constant for lutetium-177 under the assumption of complete local  $\beta$ -absorption, consistent with prevailing practice.

Individual and mean absorbed radiation dose to CSF and blood will be summarized using descriptive statistics for all patients in the Dosimetry Analysis Set and by trial site.

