**Methodology/trial design:**

This is a Phase I/II, open-label, safety and efficacy trial in pediatric and adolescent patients (3 to 19 years) with recurrent or refractory medulloblastoma.

Part 1 will be a dose-escalation phase with a 3+3 sequential-group design (except for the first dose level, which will consist of a single patient only), in which patients will receive a maximum of two 5-week cycles of treatment with intracerebroventricular Lu-DTPA-omburtamab. A Data Monitoring Committee will review the safety data from previous dose levels and provide recommendations on whether dose escalation should continue. In Part 1, Cycle 1 will comprise a dosimetry dose on Day 1 and a treatment dose on Day 8, while Cycle 2 will comprise a treatment dose on Day 1. Successive dosing groups will receive escalating treatment doses of lutetium-177 conjugated to a fixed mass dose of approximately 1 mg DTPA-omburtamab; the dosimetry dose will be fixed for all patients.

Part 2 will be a cohort-expansion phase in which patients will receive a maximum of 5 cycles of intracerebroventricular Lu-DTPA-omburtamab at the RP2D determined in Part 1. All cycles in Part 2 will comprise a treatment dose on Day 1.

The AEs will be evaluated according to CTCAE version 5.0.

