- Data from the I-omburtamab trials indicate that although myelosuppression was the main non-dose-limiting AE, radioimmunotherapy was well tolerated even after treatment with external beam craniospinal radiation and a boost to the primary site, which contribute 28 and 24 Gy, respectively, while I-omburtamab resulted in a mean CSF absorbed dose of 0.60 Gy/mCi (0.17 to 2.07 Gy/mCi). I-omburtamab therapy corresponds to less than 30% of the total radiation received by these patients. Animal-based dosimetry predicts a dose to the brain of 13.2 and 14.4 cGy/10 mCi for Lu-DTPA-omburtamab and I-omburtamab respectively. The higher absorbed doses reported in patients may be due to the difference in measuring brain versus CSF and reflect the presence of tumor in patients versus naïve animals.

Nevertheless, to confirm our hypothesis, a follow-up study in nude mice evaluating extended (8 weeks) radiotoxicity, and in particular, the threshold and reversibility of myelosuppression after administration of 100 or 200 µCi Lu-DTPA-omburtamab or 100 µCi I-omburtamab has been conducted. These doses correspond to 40 and 80 mCi on a body weight basis for a 10-kg child. At 5 weeks post dose, no adverse findings have been noted as measured by mortality, morbidity, clinical signs, body weights, or clinical chemistries. Results show that lower levels of radioactivity are not associated with significant myelosuppression. There was no significant group differences in body weight. At 1 week post dose, red blood cell counts and hematocrit were decreased in animals given 200 µCi Lu-DTPA-omburtamab, and these changes showed continued recovery at 2 through 5 weeks post dose.

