#### **4.4. *Data Monitoring Committee***

An external DMC will be established to assure patient safety and will function independently of all other individuals associated with the conduct of the trial, including site investigators participating in the trial. The DMC will consist of a minimum of 2 physicians whose expertise covers relevant specialties.

During the conduct of Part 1, following completion of the first 5-week treatment cycle (Cycle 1) for the last patient in each dose level, the DMC will evaluate available safety information and recommend trial continuation or termination. If continuation is recommended, the DMC will recommend to the sponsor whether the dose should be escalated, de-escalated, or held at the same level. In the absence of DLT during the first two weeks of the first patient enrolled in each dose level, the enrollment to the dose level will continue without the need of feedback from the DMC.

If any of the side effects mentioned in the DLT definitions ([Section 3.1.1.2](#)) occurs during Cycle 2 in Part 1, these will be discussed at the first upcoming preplanned DMC meeting, and the internal Sponsor Safety Committee will evaluate the external DMC recommendations for further dosing. During Part 1 and until the DMC meeting in Part 2, the sponsor will share with the DMC all SAEs occurring during the trial and an unplanned DMC meeting can be held at the request of either the DMC or the Sponsor Safety Committee.

The DMC will evaluate the totality of cumulated absorbed dose calculated based on the dosimetry data from Part 1, and all available DLTs and other non-DLT toxicities from cycles 1 and 2 in all patients dosed in Part 1, to guide whether the maximum of five cycles is feasible in Part 2.

During the conduct of Part 2, an additional DMC meeting will be held when the eighth patient has completed dosing in Cycle 1 to evaluate whether the trial should be modified, stopped, or continue unchanged. The Sponsor Safety Committee will evaluate the recommendations from the DMC after each DMC meeting. Any significant finding/recommendation from the DMC and endorsed by the Sponsor Safety Committee will be communicated to the regulatory authorities and Institutional Review Board (IRB)/Ethics Committee (EC) as appropriate, and to the sites.

Responsibilities, procedures, content of the DMC packages, and workflow of the DMC are specified in the DMC Charter.

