## Absorbed Radiation Doses in CSF and Blood

The radioactivity in CSF and blood after administration of the dosimetry dose (seven measurements) and treatment dose (one measurement) in Part 1 Cycle 1 will be measured at site using a scintillation well counter, following qualified procedures outlined in the technical operations manual. The patients will have approximately 0.5 mL of CSF and 2 mL of peripheral blood drawn at each timepoint mentioned in [Table 4](#).

Upon local analysis, the data will be transferred to a vendor located in US for central evaluation of the radiation doses delivered to the CSF and blood (derived from radioactivity versus time data).

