## **8.7. Dosimetry Analysis (Part 1 only)**

Spinal cord, brain, and non-target region of interest absorbed radiation doses will be estimated and CSF mean absorbed radiation doses will be calculated on the basis of whole-body planar gamma camera scans. Tumor target absorbed doses will be calculated on the basis of SPECT scan, if possible. Additionally, the mean absorbed radiation dose in CSF and blood will be calculated from CSF and blood radioactivity measured in CSF and blood samples taken at predefined timepoints after the dosimetry and the treatment doses in Cycle 1.

Individual and mean dosimetry data will be calculated per trial site and will be summarized using descriptive statistics.

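### Sections 8.6 and 8.7 pool absorbed dose over patients and sites without naming the infusion covered or normalising to administered activity

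*Combined protocol and SAP*

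**What the plan says.** Section 8.6 derives CSF and blood absorbed dose from samples "taken at predefined timepoints after the dosimetry and the treatment doses in Cycle 1". It then states: "Individual and mean absorbed radiation dose to CSF and blood will be summarized using descriptive statistics", and the groupings it gives are "for all patients in the Dosimetry Analysis Set and by trial site". Section 8.7 does the same for organ dosimetry: "Individual and mean dosimetry data will be calculated per trial site and will be summarized using descriptive statistics". The synopsis repeats both rules.

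Neither section normalises to administered activity or tabulates by dose level, age or weight. Section 8.3 prescribes geometric mean and geometric CV for log-normal data, but no dose normalisation. Residence time (Sections 2.2.2.1 and 8.6) is expressed in µCi·h/g, which also rises with the activity given.

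On the infusions themselves, the synopsis says "the dosimetry dose will be fixed for all patients". Section 3.1.1 sets it at 5 mCi, with a possible increase to 10 mCi for later patients. Planned treatment activities are 10, 25, 50, 65 and 85 mCi. Section 7.2.2 describes CSF and blood counting "after administration of the dosimetry dose (seven measurements) and treatment dose (one measurement) in Part 1 Cycle 1".

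On use of the result, Section 4.4 says: "The DMC will evaluate the totality of cumulated absorbed dose calculated based on the dosimetry data from Part 1", as part of judging whether five cycles are feasible in Part 2. Section 3.1.3 describes the same role, and Section 5.3.1 lets the Part 1 absorbed-dose findings guide dose reductions in Part 2.

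**The concern.** Absorbed dose scales with the activity given, and Part 1 is designed to vary that activity. A mean in Gy over all patients is a clear quantity only if everyone received the same activity or if each value is divided by activity first. Section 8.6 uses data from one infusion that is nominally the same for everyone and one that varies 8.5-fold, and does not say whether the summary refers to the first, the second or their sum. Two analysts could follow the text and report very different numbers.

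The stake is practical. Part 1 dosimetry is a secondary endpoint, but it is to be carried forward to a cumulated dose at the RP2D over as many as five cycles. That projection needs dose per unit activity. The protocol's own background uses that scale: Section 1.2.3 says the iodine-131 product "resulted in a mean CSF absorbed dose of 0.60 Gy/mCi", and Table 1 is given per MBq and per mCi for a stated body size (19 kg). Patients aged 3 to 19 years receive flat activity, so body size is an obvious source of variation in Gy/mCi, and no display of it is planned.

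**Working it through.** **The plan's own figure.** Section 8.1 gives up to 25 patients for Part 1. One patient at Dose Level 1 plus four levels of six gives 1 + 4 × 6 = 25, so the figure reproduces. With no expansions the count is 1 + 4 × 3 = 13. The documents state no precision target for dosimetry.

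**Inputs.** Treatment activities and the 5 mCi dosimetry dose are from Section 3.1.1, the sampling schedule from Table 4, the lutetium-177 half-life of 6.65 days from Table 2, and about 9 Part 1 sites from the synopsis. Assumptions: absorbed dose is proportional to activity, every patient analysed received both infusions, and no intermediate level is added.

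**Which infusion supplies the data.** In Table 4, seven post-dose CSF/blood samples follow the dosimetry dose (30 min, 1, 4, 24, 48 and 72 h, Day 5–7) and one follows the treatment dose (Day 15). Of the five planar scans, four follow the dosimetry dose. By physical decay alone, activity remaining on Day 15 is:
- from the 5 mCi dose, 14 days old: 5 × 2^(−14/6.65) = 1.16 mCi;
- from a 10 mCi treatment dose, 7 days old: 10 × 2^(−7/6.65) = 4.82 mCi, so the dosimetry share is 1.16/(1.16 + 4.82) = 19%;
- from an 85 mCi treatment dose: 40.98 mCi, so the share is 1.16/42.14 = 3%.

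The Day 15 sample therefore reflects mainly the treatment dose, and the earlier seven only the dosimetry dose.

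**Spread caused by activity alone.** Under proportionality, the CV of absorbed dose with identical Gy/mCi in everyone equals the CV of activity (sample SD divided by mean).

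| Dose summarised | Allocation over levels | Mean (mCi) | SD | CV |
|---|---|---|---|---|
| Treatment | 1/3/3/3/3 (n = 13) | 685/13 = 52.7 | 25.4 | 48% |
| Treatment | 1/6/6/6/6 (n = 25) | 1360/25 = 54.4 | 23.8 | 44% |
| Dosimetry + treatment | 1/3/3/3/3 | 57.7 | 25.4 | 44% |
| Dosimetry + treatment | 1/6/6/6/6 | 59.4 | 23.8 | 40% |
| Dosimetry only, all at 5 mCi | any | 5.0 | 0 | 0% |
| Dosimetry only, 6 of 25 at 10 mCi | – | 6.2 | 2.18 | 35% |
| Dosimetry only, 12 of 25 at 10 mCi | – | 7.4 | 2.55 | 34% |

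The 0% ignores the accepted range of 4.5 to 5.5 mCi in Table 3. With 25 patients, the pooled mean treatment activity is 54.4/10 = 5.4 times the lowest level and 54.4/85 = 0.64 times the highest.

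**What the ambiguity does to the reported number.** As an illustration only, take 0.60 Gy/mCi, the iodine-131 CSF figure in Section 1.2.3 (range 0.17 to 2.07).
- Dosimetry infusion only: 0.60 × 5 = 3.0 Gy for everyone (0.85 to 10.35 Gy over the range).
- Treatment infusion only: 6, 15, 30, 39 and 51 Gy by level; pooled mean 0.60 × 54.4 = 32.6 Gy (9.2 to 112.6 Gy over the range), with an SD of 0.60 × 23.8 = 14.3 Gy from activity alone.
- Sum of both: 9 to 54 Gy; pooled mean 0.60 × 59.4 = 35.6 Gy.

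All three are permitted by the wording. Expressed per mCi, the activity component of the spread falls to zero under proportionality and only between-patient variation remains.

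**By site.** With 9 sites the average is 13/9 = 1.4 to 25/9 = 2.8 patients per site, possibly at different dose levels.

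**The case against.** A reader might infer that the main dosimetry result simply mixes 10 to 85 mCi and cannot be interpreted. The documents do not support that, for four reasons.

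First, most of the data come from the common infusion. The Dosimetry Analysis Set is defined by receipt of the dosimetry dose, and seven of the eight post-dose samples follow it. The method in Section 8.6, trapezoidal integration with a fitted exponential tail, could not be run on one post-treatment sample alone. If the summary is meant for the dosimetry infusion, it pools cleanly across dose levels unless the activity is switched. The CVs above 40% then do not apply.

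Second, individual values are to be reported, and Section 5.2 requires infused activity to be measured from the syringe before and after each infusion. Gy/mCi for an infusion is then one division per patient.

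Third, nothing shows that the DMC would see only a pooled mean. Section 4.4 leaves package content to the DMC Charter, which was not available, and Section 3.1.3 speaks of an expected cumulated dose, which is already a projection. No planned analysis compares the results with the 0.60 Gy/mCi background figure either.

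Fourth, by-site output has a reason: counting and scanning are done at each site. Dose-level groups would also be small, at one to six patients.

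All of this stands, and it limits the point. It does not remove it. The text still names both infusions without saying which one is summarised, and gives no rule for reaching the treatment dose from the dosimetry curve. The technical operations manual cited in Section 7.2.2 may cover estimation, but Section 8 does not refer to it for the summaries.

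**Conclusion.** The concern holds as an unspecified and poorly suited summary rule, not as a loss of information. If the summary covers the fixed 5 mCi infusion alone, pooling is sound. If it includes the treatment dose, the pooled absolute mean depends on enrolment per level, with an activity-driven CV of about 44% to 48% for treatment alone and 40% to 44% for dosimetry plus treatment. If it spans a switch to 10 mCi, the dosimetry-only CV is about 34% to 35% in the two scenarios shown.

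These sizes rest on proportionality of absorbed dose to activity, on the assumed allocations, and on every patient receiving both infusions. Patients who stop after the dosimetry dose are replaced (Section 4.3.4) but could remain in the Dosimetry Analysis Set, which is one more reason to name the infusion.

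The endpoint is secondary and descriptive. The change is still worth making, because the result feeds the projection of cumulated radiation dose that guides the number of Part 2 cycles.

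**What to change.** In Sections 8.6 and 8.7 and the matching synopsis text:
- state for each summary whether it covers the dosimetry infusion, the treatment infusion or their sum, and state the rule if treatment-dose values are scaled from the dosimetry curve;
- make absorbed dose per measured administered mCi the pooled summary, with geometric mean and geometric CV as Section 8.3 already provides for log-normal data;
- report absolute absorbed dose by dose level;
- list or plot Gy/mCi against age or weight, labelled exploratory;
- keep the by-site output as a measurement quality check.

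Activity, age and weight are already collected, so the cost is wording and a few descriptive tables. The drawback is that the dose-level groups are small, so those tables will be close to listings.

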## **8.7. Dosimetry Analysis (Part 1 only)**

Spinal cord, brain, and non-target region of interest absorbed radiation doses will be estimated and CSF mean absorbed radiation doses will be calculated on the basis of whole-body planar gamma camera scans. Tumor target absorbed doses will be calculated on the basis of SPECT scan, if possible. Additionally, the mean absorbed radiation dose in CSF and blood will be calculated from CSF and blood radioactivity measured in CSF and blood samples taken at predefined timepoints after the dosimetry and the treatment doses in Cycle 1.

Individual and mean dosimetry data will be calculated per trial site and will be summarized using descriptive statistics.

## **8.8. Pharmacokinetic Analysis**

The serum and CSF PK parameters of Lu-DTPA-omburtamab following the treatment doses in Cycles 1 and 2 will be calculated using standard noncompartmental methods in both study parts. Standard PK parameters (such as Cmax, AUC, half-life) will be calculated.

## **8.9. Interim Analysis**

*Ad hoc* interim analyses will be performed in connection with communication with regulatory authorities.

## 10. APPENDICES

### Appendix 1: Clinical Laboratory Evaluations

The following clinical laboratory analytes will be assessed locally at the site:

Chemistry:	Hematology (CBC):
Albumin	Hematocrit
ALP	Hemoglobin
ALT	MCH
AST	MCHC
BUN	MCV
Calcium	Platelet count
Chloride	Red blood cell (RBC) count
Creatinine	White blood cell (WBC) count
Glucose	WBC differential
LDH	(% & absolute):
Potassium	Basophils
Sodium	Eosinophils
Total bilirubin	Lymphocytes
Total CO 2 (measured as bicarbonate)	Monocytes
Total protein	Neutrophils
Triglycerides	
Uric acid	For females of childbearing potential only:
CSF	Urine or serum pregnancy test (only at the timepoints indicated in Appendix 3 )
Total protein	
Glucose	
Cell count	
Cytology	

Abbreviations: ALP = alkaline phosphatase; ALT = alanine aminotransferase; AST = aspartate aminotransferase; BUN = blood urea nitrogen; CBC = complete blood count; CO2 = carbon dioxide; LDH = lactate dehydrogenase; MCH = mean corpuscular hemoglobin; MCHC = mean corpuscular hemoglobin concentration; MCV = mean corpuscular volume; RBC = red blood cell; WBC = white blood cell.

If clinical signs of infection are observed following IMP infusion, the drawn CSF and blood samples must be cultured at the local microbiological laboratory.

## Appendix 2: Regulatory, Ethical, and Trial Oversight Considerations

### Regulatory and Ethical Considerations

This trial will be conducted in accordance with the protocol and with the following:

- Consensus ethical principles derived from international guidelines including the Declaration of Helsinki and Council for International Organizations of Medical Sciences International Ethical Guidelines
- Ethical considerations for clinical trials on medicinal products conducted with minors
- Applicable International Council for Harmonisation (ICH) Good Clinical Practice (GCP) Guidelines
- Applicable laws and regulations.

The protocol, protocol amendments, patient information, ICF, investigator's brochure, and other relevant documents (e.g., advertisements) must be submitted to an Institutional Review Board (IRB)/Ethics Committee (EC) by the investigator and reviewed and approved by the IRB/EC before the trial is initiated.

- Any amendments to the protocol will require regulatory and IRB/EC approval before implementation of changes made to the trial design, except for changes necessary to eliminate an immediate hazard to trial patients.

The investigator will be responsible for the following:

- Ensuring the trial is conducted in accordance with the procedures and evaluations described in this protocol. Deviations from the protocol should not occur. If deviations do occur, the investigator has to inform the CRA for discussion and decision on required action(s). Deviations should be documented in writing including an explanation. Documentation of deviations will be filled in the investigator's site file and a copy in the Sponsor's file. Depending on the nature of the deviation, this may be reported to the appropriate regulatory authority
- Providing written summaries of the status of the trial to the IRB/EC annually or more frequently in accordance with the requirements, policies, and procedures established by the IRB/EC
- Notifying the IRB/EC of serious adverse events or other significant safety findings as required by IRB/EC procedures
- Providing oversight of the conduct of the trial at the site and adherence to requirements of 21 Code of Federal Regulations (CFR), ICH guidelines, the IRB/EC, European regulation 536/2014 for clinical studies (if applicable), and all other applicable local regulations.

## Finances and Insurance

Financing and insurance will be addressed in a separate agreement. Insurance and liability will be in accordance with applicable local laws and regulations and GCP.

## Informed Consent

The investigator or his/her designee must obtain the written informed consent from each patient, and/or the patient's acceptable authorized representative, before any trial-related procedures are performed, as applicable to local regulations. If the indwelling intracerebroventricular access device (e.g., Ommaya) is placed in connection with the tumor resection, the informed consent must be obtained prior to the surgery, and before the start of the screening period. However, if this is placed as part of a standard of care at site, this is not considered as a trial procedure and hence not requiring informed consent prior to the procedure. A separate ICF will be issued for the circulating tumor DNA (ctDNA) and primary tumor DNA assessments, for patients who wish to consent to that analysis. The written patient information must not be changed without prior discussion with the sponsor and approval by the IRB/IEC. Participant and legal representative (e.g., parent[s] or guardian[s]), if applicable, must receive full trial information, both verbally and written, before consent is given. A child or adolescent patient will be informed and included in the conversations with the parents, to the extent that he/she can understand given his/her age. A patient information sheet will be prepared addressing legal representative(s) and a version especially addressing the adolescent population will also be prepared, as and when applicable to local regulations.

The patient information will contain full and adequate information regarding the objective and procedures of the trial and the possible benefits and risks involved. This will include any information of possible transfer of biological materials, imaging, and other needed for central analysis. The consent shall be given in interest of the child, meaning that he/she is presumed willing to participate. Regardless of legal representative(s) written consent, the participation shall not take place if the patient objects. Objection can also be non-verbal and expressed by the child's attitude, body language, or resistance. Informed consent (parents or legal representative), and if applicable informed assent (child/adolescent), must be signed in accordance with local regulations. The patient information will be updated in case of new information that may affect a patient's decision to participate in or remain in the trial.

If applicable to local regulations: if a child turns 18 during his/her participation in the trial, a written consent must be obtained from him/her before the trial can continue.

Before signing the ICF, the patient/parents must be given sufficient time to consider the possible participation. Further, each patient must be informed about their right to withdraw from the trial at any time. Parents and patients will also be informed that research participation is voluntary but if they withdraw from the trial, their data will still be used. When the ICF has been signed, the patient/parent(s) receives a copy of the signed form and the original is retained in the investigative site file. A second copy may be kept in the patient's medical notes. The ICFs must be signed and dated both by the signee and by the person providing the information to the patient/parents. It is recommended to notify the patient's family doctor of the patient's consent to participate in the trial.

Informed consent must be obtained before any trial-related procedures. The placement of the indwelling intracerebroventricular access device (e.g., Ommaya reservoir) is a surgical procedure requiring general anesthesia. Having the neurosurgeon place the Ommaya in association with the anesthesia induced for the surgical resection of the tumor will reduce the burden of the trial procedures by avoiding an extra surgical procedure. Another consideration is that since the patient may receive high-dose chemotherapy in the period leading up to the screening period, this may be associated with myelosuppression rendering an invasive procedure like Ommaya placement not feasible. There is, therefore, a rationale for allowing placement of the Ommaya reservoir prior to screening for patients who are potential candidates for trial participation, in particular for patients who are not being resected to R0 classification. In cases where the potential patient is a referral patient, the investigator should discuss trial inclusion and exclusion criteria with the referring physician, and only patients deemed eligible for the trial should be considered for Ommaya placement in connection with tumor resection. In this case, the informed consent must be obtained prior to the surgery, and may be done so up to 2 months before the start of the screening period.

